For the spectacle wear secondary endpoints based on binocular measurements, the primary analysis population will be a modified Intent-to-Treat (mITT) analysis that only includes subjects randomized and binocularly implanted with the same lens model (either investigational or control lenses in both eyes). Any missing values at the 6-month postoperative visit will be imputed in ITT and mITT analyses.

Since there are no inferential statistics for the monocular defocus curve secondary endpoint, a safety population (SP), with available data (i.e., no data imputation) and with subjects randomized and implanted with either an investigational or control lens will be the primary analysis population. The SP will also be used for safety endpoints and other endpoints. With the exception of spectacle wear data, binocular, second-eye and pooled eye data will be considered supplementary and will be used for secondary analyses. Per-protocol analysis will be performed for primary and secondary endpoints. Sensitivity analysis will also be performed for primary DCNVA (40 cm) endpoint and secondary DCIVA, DCNVA (33 cm), BCDVA, and spectacle wear endpoints. Please see detailed descriptions of the analysis populations in Section 20.1.

All data will be reported by IOL group.

STUDY VISITS AND PROCEDURES:

Inclusion and exclusion qualifications will be assessed at the preoperative visit according to the inclusion/exclusion criteria. The Informed Consent Form and Authorization for Use/Disclosure of Health Information form (HIPAA authorization) must be signed by any patients who agree to participate in the study prior to undergoing any study-specific procedures. Those subjects who meet the inclusion/exclusion criteria and agree to participate will be randomized to a treatment group in a masked fashion and implanted in both eyes: either the test Model ZFR00V IOL or control Model ZCB00 IOL. The eye implanted first will be considered the primary study eye. All subjects are intended to have bilateral cataract surgery with the second-eye surgery occurring after the 1-week exam for the first eye but no more than 30 days after the first eye surgery. Study subjects as well as personnel performing the postoperative vision testing and refractions

will be masked for the duration of the study. In addition, key Sponsor personnel will be masked during the study, as necessary.

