4. MONOCULAR DISTANCE-CORRECTED DEFOCUS CURVE

Success Criteria: The mean distance-corrected visual acuity for the investigational lens group is maintained at 0.2 LogMAR or better from 0.0 D to -2.5 D of defocus.

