For the primary DCNVA (at 40 cm), secondary BCDVA, DCIVA, DCNVA (at 33 cm) and spectacle wear endpoints, the mITT, sensitivity, PP and safety populations will be used for data reporting. For defocus curve secondary endpoint, only safety and PP populations will be used for data reporting. For safety endpoints and other endpoints, only the safety population will be used. The primary analysis will be based on first eye data, unless stated otherwise. However, select data such as some visual acuity variables will also be reported separately for second eyes as supportive data only. Safety (adverse events, medical and lens findings, and non-directed visual symptoms) and effectiveness endpoints (monocular DCNVA (at 40 and 33 cm), BCDVA and DCIVA) and monocular mesopic DCNVA will also be evaluated using all eyes (pooling both first and second eyes together) as supportive analysis. Descriptive statistics will be presented for analyses of all eyes.

⁵ Rom D and B. Holland. (1995). A new closed multiple testing procedure for hierarchical families of hypotheses. *Journal of Statistical Planning and Inference* 46:265-275

⁶ Rom D, R. Costello, and L. Connell. (1994). On closed test procedures for dose-response analysis. *Statistics in Medicine* 13:1583-1596

⁷ Marcus R, E. Peritz, and K. Gabriel. (1976). On closed testing procedures with special reference to ordered analysis of variance. *Biometrika* 63:655-660.

⁸ Huque M and A Sankoh. (1997). A reviewer's perspective on multiple endpoint issues in clinical trials. *Journal of Pharmaceutical Sciences* 7:545-564.

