2 ANALYSIS POPULATIONS

2.1 ANALYSIS POPULATIONS/HANDLING OF MISSING DATA

For the primary effectiveness endpoint (DCNVA at 40 cm) and monocular secondary effectiveness endpoints (DCIVA, DCNVA (at 33 cm), and BCDVA),

For eyes that do not have data available at the 6-month postoperative visit, data will be imputed for the mITT analyses. For continuous variables (DCNVA, BCDVA and DCIVA), the planned method to use is the MCMC full-data imputation as described in Little & Rubin².

A Per-Protocol (PP) analysis will also be presented for primary effectiveness and secondary endpoints. The PP population for monocular data will include eyes with an investigational or control lens implanted, evaluated within the proper study interval and without clinically-relevant protocol deviations (deviations that could potentially impact the primary or secondary endpoints) as determined prior to database lock. The PP population for binocular data will include subjects that do not have any of the deviations stated above in either eye. PP tables will include available data at the time of analysis (i.e., no data imputation).

The safety population for monocular variables will consist of all eyes implanted with either a test or control IOL(s) and with data available at the time of analysis (i.e., no data imputation). The safety population for binocular variables will consist of all subjects implanted with the same test or same control IOLs in both eyes and with data available at the time of analysis (i.e., no data imputation). For secondary monocular defocus curve, safety population will be used for the primary analysis since there is no inferential statistics required for that endpoint. For all safety endpoints and other endpoints, the safety population will be used. For BCDVA percent 20/40 or better vs. ISO SPE rate, a best-case population will also be used, consisting of eyes in the safety population without any clinically-relevant preoperative ocular pathologies or macular degeneration detected at any time.

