2.4 RANDOMIZATION

If a surgeon implants the wrong study lens, i.e., other than the one on the randomization schedule, the subject's study data will be analyzed according to the randomization schedule in the mITT population and will be analyzed according to the lens received in the safety population. The subject will be excluded from the Per-Protocol population analysis. If a surgeon implants a non-study IOL (e.g., due to capsule rupture prior to IOL implantation) or if the surgery is canceled in the few days between randomization and surgery (e.g., due to death, illness), the subject will not be part of the mITT, safety or Per-Protocol populations but will be placed in the intended IOL group (IOL group based

on randomization schedule) and included in the analyses.

sensitivity

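### The defocus-curve pass/fail criterion is judged only on available data; having no hypothesis test does not justify this, because selective loss would move the mean itself

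*Protocol*

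**What the plan says.** Protocol 6.2, item 4, sets the success criterion: "The mean distance-corrected visual acuity for the investigational lens group is maintained at 0.2 LogMAR or better from 0.0 D to -2.5 D of defocus". It is a point threshold on one group's mean, to be met across the range.

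The Synopsis (Data Analysis) chooses the population on this ground: "Since there are no inferential statistics for the monocular defocus curve secondary endpoint, a safety population (SP), with available data (i.e., no data imputation". It makes that set the primary one for the endpoint. SAP 2.1 agrees: "For secondary monocular defocus curve, safety population will be used for the primary analysis since there is no inferential statistics required for that endpoint". Protocol 20.1 closes off other sets: "For defocus curve secondary endpoint, only safety and PP populations will be used for data reporting". SAP 2.1 has the same restriction and adds that per-protocol tables use available data without imputation.

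The primary endpoint and the other four secondary effectiveness endpoints are treated differently. Their primary set is mITT, and the Synopsis says "Any missing values at the 6-month postoperative visit will be imputed in ITT and mITT analyses". It also says "Sensitivity analysis will also be performed for primary DCNVA (40 cm) endpoint and secondary DCIVA, DCNVA (33 cm), BCDVA, and spectacle wear endpoints". Defocus is not in that list.

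On wrong-lens implants, SAP 2.4 keeps the randomised assignment in the mITT set, whereas such a subject "will be analyzed according to the lens received in the safety population".

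**The concern.** A hypothesis test and a threshold on a mean are exposed to selective missing data in the same way, because both start from the mean. Leaving out the p-value removes a statement about sampling error. It does not make the eyes that were measured representative of the eyes that were implanted.

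The plan does not apply its own reason consistently. In Protocol 6.1 and 6.2, the 0.2 LogMAR clinical-significance criteria for DCNVA at 40 cm, DCIVA at 66 cm and DCNVA at 33 cm are also thresholds on the test-group mean, and the visible text attaches no test to them. Those endpoints are nevertheless assigned to mITT.

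Loss related to outcome is plausible. Protocol 10.8 discontinues a subject once the study lens (if unilateral) or both study lenses (if bilateral) are removed, and poor vision may also affect who returns or completes the test. At stake is a named success criterion that could be met in the observed eyes although it would be missed in all implanted test eyes, with nothing planned for this endpoint that would show it.

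**Working it through.** **Inputs from the documents** (Protocol 20.7, SAP 7): 150 enrolled per group, 10% screen failure, 10% dropout, 135 implanted and 122 evaluable per group. The threshold is 0.2 LogMAR (Protocol 6.2). The SD of 1.6 lines is stated for DCNVA at 40 cm.

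**Assumptions:** the documents give no expected defocus mean or SD. Observed means are therefore shown as a range, and the DCNVA SD (0.16 LogMAR) is borrowed where an SD is needed. One line is 0.1 LogMAR.

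**1. The plan's own figures.** 150 × 0.9 = 135, and 135 × 0.9 = 121.5, about 122: reproduced. DCNVA power with 122 per group, difference 0.7 line, SD 1.6 lines, one-sided 0.025: Φ(0.7 / (1.6 × √(2/122)) − 1.96) = Φ(1.46) = 92.7%, which agrees with the stated figure of over 90%.

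**2. Missing fraction.** f = (135 − 122)/135 = 13/135 = 0.0963.

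**3. Shift in the mean.** If missing eyes are d worse than observed eyes, the full-group mean exceeds the observed mean by f × d:
- d = 0.1 (1 line): 0.010
- d = 0.2 (2 lines): 0.019
- d = 0.3 (3 lines): 0.029

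**4. Tipping point.** For an observed mean m that passes, the full-group mean exceeds 0.2 when d > (0.2 − m)/f.

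| Observed mean at the worst step | Missing eyes must be worse by more than |
|---|---|
| 0.195 | 0.5 line |
| 0.19 | 1.04 lines |
| 0.18 | 2.1 lines |
| 0.17 | 3.1 lines |
| 0.15 | 5.2 lines |

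Other missing rates (assumed), at m = 0.19: with 7/135 = 5.2% missing, 1.9 lines are needed; with 27/135 = 20% missing, 0.5 line.

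**5. Illustration for a single worst step.** SE = 0.16/√122 = 0.0145. Suppose the true mean of all implanted test eyes is 0.21, a fail. The available-data mean still passes with probability Φ((0.2 − (0.21 − f × d))/0.0145): 25% with d = 0, 49% with d = 0.1 and 74% with d = 0.2. This measures the effect of selective loss, not the gain from imputation.

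**6. Analysis by lens received.** One test-randomised eye that received the control lens and is 0.2 to 0.4 LogMAR worse (assumed) moves the mean by 0.2/135 to 0.4/135, that is 0.0015 to 0.003.

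**The case against.** The strongest reply is that this is a single-arm description of lens performance and that the plan already holds a cross-check. Protocol 20.1 and SAP 2.1 report DCNVA at 40 and 33 cm, DCIVA and BCDVA in the mITT, sensitivity, per-protocol and safety populations. The gap between their imputed and available-data means will show how much missing data matter near 2.5 D, 3 D, 1.5 D and at distance. The SAP also reports counts of missing and out-of-window eyes (2.2, 3.1). This stands as a partial safeguard and lowers the priority. It neither decides the defocus criterion nor covers every step.

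A second reply is that imputation helps least where it is most needed. Subjects who drop out have no same-visit acuities to predict from, and MCMC imputation assumes missing at random. That is correct. It means mITT alone is not enough; it does not support relying on available data alone.

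A reader might also infer four stronger points that the documents do not support:
- **That the mean is biased.** It is biased only if missingness relates to outcome. The rule on lens removal makes that plausible but does not show it.
- **That analysis by lens received is a material flaw.** Step 6 shows it is negligible unless wrong-lens implants are frequent. The mITT set also leaves out subjects who are not implanted or who receive a non-study lens, so the comparison is with eyes randomised and implanted, not with everyone randomised.
- **That the -2.5 D step and the 40 cm test are one quantity judged under two rules.** The nominal demand matches (1/0.40 m = 2.5 D), but Protocol 10.7 tests defocus at 4.0 m with no adjustment for test distance. The two results could differ in identical eyes.
- **That withheld text might contain the missing analysis.** The sentence restricting defocus to safety and per-protocol is legible in both documents.

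**Conclusion.** The concern holds in a limited form. The absence of a test is not a valid reason for judging a mean-based success criterion only on available data, and no planned analysis examines missing data for this endpoint.

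The consequence is bounded. At the planned 9.6% missing, a pass reverses only if the worst step between 0.0 and -2.5 D lies within about 0.01 to 0.03 LogMAR of the threshold and the missing eyes are about 1 to 3 lines worse. At an observed mean of 0.15 the required 5.2 lines is implausible. These tipping points rest on the plan's attrition and on assumed observed means; only the pass probabilities in step 5 need the borrowed SD. This is a worthwhile, inexpensive improvement, not a defect that undermines the trial.

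**What to change.** In Protocol Synopsis (Data Analysis), Protocol 20.1 and SAP 2.1:
- Evaluate the criterion at each step from 0.0 to -2.5 D in the mITT first-eye set: randomised and implanted, grouped as randomised, with the MCMC imputation planned for the other acuities and the eye's available fixed-distance acuities in the imputation model.
- Add a tipping-point sensitivity analysis that makes the imputed test-group values progressively worse until the verdict changes, because MCMC imputation assumes missing at random.
- Report N and a 95% CI at each step.
- State in advance how eyes whose study lens was removed enter this analysis, since imputing a curve for a removed lens is an estimand choice.
- Keep the safety and per-protocol curves alongside, and delete the rationale based on the absence of inferential statistics.

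The cost is wording in two documents and extra imputation runs. No new data are needed. The reported means may become slightly less favourable.

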2. BACKGROUND/INTRODUCTION

Presbyopia, defined as the age-related loss of accommodative amplitude¹, affects essentially all human beings beyond the age of 45 and impacts the ability of the eye to focus at near distances². Current intraocular lens options for cataract patients who desire improved vision across a range of distances include a choice of monovision or multifocality. Patients implanted with standard monofocal lenses often need spectacles for reading or performing other near tasks, even if a monovision option is selected. Patients implanted with multifocal lenses, while being able to read and perform other near tasks without spectacles, may have limited intermediate ability (e.g., may need spectacles to work on a computer), and may sometimes experience dysphotopsias (e.g., halos), particularly at night. Some accommodating lenses are also available on the market, although their effect depends upon fit within the capsular bag or capsular bag elasticity. The extended range of vision IOL, TECNIS Symfony Model ZXR00, uses diffractive technology to elongate the depth of focus and improve vision range compared to standard monofocal IOLs.

The investigational IOL in this protocol, Model ZFR00V, is a next-generation TECNIS lens that is designed to provide an increased range of vision for intermediate and near tasks as compared to the control IOL Model ZCB00.

3. CLINICAL HYPOTHESIS

The investigational IOL Model ZFR00V will provide improved distance-corrected near visual acuity, as well as decreased spectacle wear compared to the monofocal control, TECNIS 1-piece IOL Model ZCB00. The mean best-corrected distance acuity of the

¹ Koretz J.F., Kaufman P.L, Neider M.W. Goeckner P.A. Accommodation and Presbyopia in the Human Eye – Aging of the Anterior Segment. *Vision Res.* 1989;29: 1685-1692.

² Benjamin, William, J., Borish, Irvin M. *Borish's Clinical Refraction*, Philadelphia: 1998, W.B. Saunders, pg 109.

investigational IOL Model ZFR00V will be non-inferior to that of the monofocal control IOL Model ZCB00.

Complication and adverse event rates associated with the investigational IOL Model ZFR00V will be within the rates for posterior chamber IOLs given in ISO 11979-7:2018.

4. STUDY DESIGN

This study is a 6-month, prospective, multicenter, three-way masked (Sponsor, subject and evaluator), bilateral randomized clinical investigation of the Tecnis IOL Model ZFR00V versus the Tecnis Model ZCB00 IOL.

The study will be conducted at up to 15 sites in the U.S.A. and will enroll up to 300 subjects to achieve approximately 270 bilaterally-implanted subjects, resulting in approximately 122 evaluable subjects in each lens group at 6 months. Subjects will be randomized to a treatment group in a masked fashion and be implanted with either the investigational IOL Model ZFR00V or the control IOL Model ZCB00 in both eyes. The eye implanted first will be considered the primary (monocular) study eye.

5. ACRONYMS

The following acronyms are used throughout this document:

- UCDVA: uncorrected distance visual acuity
- BCDVA: best-corrected distance visual acuity
- UCIVA: uncorrected intermediate visual acuity
- DCIVA: distance-corrected intermediate visual acuity
- UCNVA: uncorrected near visual acuity (40 cm)
- DCNVA: distance-corrected near visual acuity (40 cm unless otherwise stated)
- D: diopters

6. STUDY OBJECTIVES AND ENDPOINTS

The purpose of this study is to evaluate the safety and effectiveness of the investigational IOL Model ZFR00V in comparison to a monofocal control IOL. The 6-month postoperative visit is the key analysis time point for all endpoints, although data will be reviewed at other time points as well. Data for other visits will be included in the final analysis.

6.1 PRIMARY EFFECTIVENESS ENDPOINT

MONOCULAR PHOTOPIC DCNVA AT 40 CM

Success criteria: Statistically significant improvement in mean monocular photopic distance-corrected near visual acuity for first eyes in the test group vs.

first eyes in the control group. In addition, clinical significance will be determined if the mean DCNVA for the test group is at least 0.2 LogMAR.

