6.2 SECONDARY EFFECTIVENESS ENDPOINTS

1. MONOCULAR PHOTOPIC DCIVA AT 66 CM

Success criteria: Statistically significant improvement in mean LogMAR distance-corrected intermediate visual acuity for first eyes in the test group vs. first eyes in the control group. In addition, clinical significance will be determined if the mean DCIVA at 66 cm for the test group is at least 0.2 LogMAR.

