2. MONOCULAR PHOTOPIC DCNVA AT 33 CM

Success Criteria: Statistically significant improvement in mean LogMAR distance-corrected near visual acuity at 33 cm for the test group compared to the control group. In addition, clinical significance will be determined if the mean DCNVA at 33 cm for the test group is at least 0.2 LogMAR.

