6.3 SAFETY ENDPOINTS

Primary Safety:

1. The rate of SSIs related to optical properties of the lens in first eyes of subjects in the test group will be analyzed using descriptive statistics and compared to that of the control group.
2. All SPE adverse events, including total SSI, reported among first eyes of subjects in the test group will be compared to ISO SPE rates.
3. All other non-SPE AEs will be analyzed using descriptive statistics comparing the two lens groups.

Co-Primary Safety:

1. The rate of monocular BCDVA 20/40 or better among first eyes of subjects in the test group will be compared to ISO SPE rates.

Additionally, secondary analyses consisting of second eyes and all investigational eyes (pooling first and second eyes together) will also be included for the above primary and co-primary safety endpoints.

Secondary Safety:

As a secondary safety endpoint, the binocular and monocular (first eyes) best-corrected distance contrast sensitivity for the test group will be compared to control (mesopic with and without glare at 1.5, 3, 6, and 12 cpd, photopic with glare at 3, 6, 12, and 18 cpd).

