8.1 INCLUSION CRITERIA

Note: All criteria apply to each eye

- Minimum 22 years of age
- Bilateral cataracts for which posterior chamber IOL implantation has been planned
- Preoperative best-corrected distance visual acuity (BCDVA) of 20/40 Snellen or worse with a glare source or 20/40 Snellen or worse without a glare source
- Potential for postoperative BCDVA of 20/30 Snellen or better
- Corneal astigmatism:
 - Normal corneal topography
 - Predicted postoperative corneal astigmatism of less than 1.00 D in both eyes, including posterior corneal astigmatism (PCA)
- Clear intraocular media other than cataract in each eye
- Availability, willingness and sufficient cognitive awareness to comply with examination procedures and study visits

- Signed informed consent and HIPAA authorization or equivalent documentation necessary to comply with applicable privacy laws pertaining to medical treatment in the governing countries
- Ability to understand and respond to a questionnaire in English

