Distance visual acuity will be measured postoperatively under photopic lighting conditions (85 cd/m², 80–110 cd/m² acceptable) using the M&S System at a test distance of 4.0 meters. For eyes unable to achieve a postoperative BCDVA of Snellen 20/40 (i.e., LogMAR 0.3, number of letters correct 70), a reason must be specified. Instructions for using the M&S System are detailed in **Appendix D**, and for distance visual acuity testing in **Appendix E**.

INTERMEDIATE VISUAL ACUITY (MASKED PROCEDURE)

Intermediate visual acuity will be measured under photopic conditions (85 cd/m², 80–110 cd/m² acceptable) using the M&S System at a test distance of 66 cm. Instructions for using the M&S System are detailed in **Appendix D** and for intermediate vision testing in **Appendix F**.

NEAR VISUAL ACUITY (MASKED PROCEDURE)

Near visual acuity will be measured at test distances of 40 cm and 33 cm under photopic conditions (85 cd/m², 80-110 cd/m² acceptable) and at 40 cm under mesopic conditions (3 cd/m²) using the M&S System.

Instructions for using the M&S System are detailed in **Appendix D** and for near vision testing in **Appendix G**.

[figure not shown]
The following near visual acuity measurements are to be performed per the visit

DEFOCUS TESTING (MASKED PROCEDURE)

Binocular and monocular (first eye) best-corrected distance defocus testing will be performed on all subjects in accordance with the methodology described in Annex F of the International Standards for Ophthalmic Implants – Intraocular Lenses Part 7 (ISO 11979-7:2018). While the testing includes plus-power defocus, the study endpoint is based upon minus-power defocus results.

Defocus testing will be performed under photopic conditions (85 cd/m², 80-110 cd/m² is acceptable) using the M&S System at 4.0 meters with the ETDRS refraction in place (no adjustment necessary for test distance).

At each defocus increment, a LogMAR visual acuity is to be obtained. Further instructions for defocus testing are detailed in **Appendix H**.

PUPIL SIZE

Pupil sizes under photopic (with and without glare), and mesopic (with and without glare) lighting conditions will be measured postoperatively during the study. For consistency, the same method of measurement should be used throughout the study.

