- Visual symptoms requiring secondary surgical intervention (e.g., lens removal)
- Tilt and decentration requiring secondary surgical intervention (e.g., repositioning)
- Residual refractive error resulting in a secondary surgical intervention
- Retained lens material resulting in secondary surgical intervention

NOTE 1: Wound “burps” during the first week postoperatively, suture removal, planned blepharoplasty, and Nd:YAG capsulotomy (for PCO) are not considered adverse events for this study.

NOTE 2: Corneal edema, and chronic anterior uveitis/iritis will be considered serious according to the guidelines listed in **Appendix O** (i.e., corneal edema resulting in BCDVA of 20/40 or worse at 1 month or later; and Grade 1+ uveitis/iritis longer than 3

months). Raised IOP, according to the guidelines listed in **Appendix O** will be considered serious if present at the last study visit (120-180 days after second eye implant).

Unanticipated Adverse Device Effect (UADE)/Unanticipated Serious Adverse Device Effect (USADE)

Any UADE (21CFR 812.3(s)) or USADE (ISO 14155) is defined as any serious adverse effect on health or safety or any life-threatening problem or death caused by, or associated with, a device, if that effect, problem, or death was not previously identified in nature, severity, or degree of incidence in the investigational plan (i.e., this protocol), application (including a supplementary plan or application), or risk assessment, or any other unanticipated serious problem associated with a device that relates to the rights, safety, or welfare of subjects.

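### The clinical-significance threshold for the primary and two secondary acuity endpoints does not state its direction, and read numerically it rewards worse vision

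*Protocol*

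**What the plan says.** Success on the primary endpoint, photopic monocular near acuity at 40 cm, has two parts in Protocol 6.1. The first is statistical superiority over the control lens. The second is a threshold on the test-group mean: "clinical significance will be determined if the mean DCNVA for the test group is at least 0.2 LogMAR".

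Two secondary endpoints in Protocol 6.2 carry the same second part:

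- Item 1, intermediate acuity: "clinical significance will be determined if the mean DCIVA at 66 cm for the test group is at least 0.2 LogMAR".
- Item 2, near acuity at 33 cm: "clinical significance will be determined if the mean DCNVA at 33 cm for the test group is at least 0.2 LogMAR".

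Item 4 of the same section, the defocus curve, uses the same number but states a direction: the test-group mean acuity "is maintained at 0.2 LogMAR or better from 0.0 D to -2.5 D of defocus".

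Other acuity limits in the protocol also state which side counts. Protocol 6.3 has "The rate of monocular BCDVA 20/40 or better among first eyes of subjects in the test group", Protocol 8.1 has "Potential for postoperative BCDVA of 20/30 Snellen or better", and Note 2 of Protocol 11.1 has "corneal edema resulting in BCDVA of 20/40 or worse at 1 month or later".

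**The concern.** LogMAR is a lower-is-better scale. A phrase meaning no less than 0.2, applied to the number, therefore sets a floor on how poor the mean must be, not a ceiling. Taken literally, the primary endpoint would be clinically significant only if the mean near acuity were 20/32 or worse, and a better-performing lens would fail.

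The literal reading is not contrived. Item 5 of Protocol 6.2 (spectacle wear) uses the same two words in its own clinical-significance clause, for a 50% proportion and a 25-percentage-point difference. There they plainly mean greater than or equal to. A programmer who gives the words one meaning throughout section 6 would code ≥ 0.20 for acuity.

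At stake is half of the stated success rule for the primary endpoint and for two secondary endpoints. A pre-specified pass/fail rule should not depend on the reader inferring which side of the threshold is a pass.

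**Working it through.** **Inputs from the documents**

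- SAP Appendix II: LogMAR = (85 − letter score)/50.
- SAP Appendix II: Snellen denominator = 20 × 10^LogMAR.
- SAP Appendix II worked examples: 78 letters gives 0.14 LogMAR, and 0.20 LogMAR gives 31.7, reported as 20/32.
- Protocol 10.7 anchor: "postoperative BCDVA of Snellen 20/40 (i.e., LogMAR 0.3, number of letters correct 70".

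**Step 1. Reproduce the documents' conversions**

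- 78 letters: (85 − 78)/50 = 0.14, as in the SAP.
- 0.20 LogMAR: 20 × 10^0.20 = 31.7, i.e. 20/32, as in the SAP.
- 70 letters: (85 − 70)/50 = 0.30, and 20 × 10^0.30 = 39.9, i.e. 20/40, as in Protocol 10.7.

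More letters give a lower LogMAR. The conversion is linear in letters, so a mean LogMAR corresponds directly to a mean letter score.

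**Step 2. Put the threshold on the letter scale**

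Letters = 85 − 50 × 0.20 = 75. The numerical reading (mean ≥ 0.20) is a mean of 75 letters or fewer, 20/32 or worse. The intended reading (mean ≤ 0.20) is 75 letters or more, 20/32 or better.

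**Step 3. Apply both readings**

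| Mean letters | Mean LogMAR | Snellen denominator | ≥ 0.20 (numerical) | ≤ 0.20 (intended) |
|---|---|---|---|---|
| 78 | 0.14 | 27.6 | not met | met |
| 75 | 0.20 | 31.7 | met | met |
| 70 | 0.30 | 39.9 | met | not met |

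The readings agree only at exactly 0.20.

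**Step 4. Check that the superiority test is not involved**

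Protocol 20.7 and SAP 7.1 claim over 90% power for a 0.7-line difference, with SD 1.6 lines, 122 per group and one-sided alpha 0.025.

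- Standard error of the difference: 1.6 × √(2/122) = 0.205 lines.
- 0.7/0.205 = 3.42, and 3.42 − 1.96 = 1.46.
- Power is 92.7% by the normal approximation and 92.6% by the noncentral t.

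The claim is reproduced. The 0.2 threshold does not enter this calculation, so rewording it changes neither power nor sample size.

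**The case against.** The strongest reply is that no competent reader would apply the harmful reading. Each clause sits under the success criteria, follows a sentence asking for improvement, and has an acuity as its subject, so it is natural to take it as at least that good. The numerical reading would also contradict the clinical hypothesis of improved near acuity in Protocol 3 and the defocus criterion for the same lens. This is right about intent, and it is why the point is modest. It does not change what the clause says, and item 5 of the same section uses the words numerically.

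A second reply is that the operative rule may lie in text that cannot be seen. Protocol 20.2 is listed in the contents but is absent from the supplied text, and what is visible of SAP 5.1, 5.2.1 and 5.2.2 is descriptive only. This stands as a limit: nothing here shows that the plan as a whole lacks a direction. If those sections already say ≤ 0.20, section 6 should match them. If they repeat the section 6 wording, the correction matters more.

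A third reply is that other acuity limits leave direction to context too. Protocol 10.7 speaks of eyes unable to achieve 20/40, and 6.2 item 3 sets non-inferiority within 0.1 LogMAR. Neither is a close parallel. Being unable to achieve a level carries its own direction, and the second is a margin on a difference, not a cut-off on an acuity.

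Finally, opposite verdicts follow from reversing any inequality, so Step 3 measures the contrast between the readings and not the chance of an error. That is fair, and no such chance is claimed.

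**Conclusion.** The concern holds as a defect of wording in Protocol 6.1 and 6.2, items 1 and 2. Read numerically, the clinical-significance clause requires a test-group mean of 0.20 LogMAR or higher (20/32 or worse), the reverse of what is evidently meant. The verdict on this half of the success rule flips for every observed mean other than 0.20.

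The practical risk is small because the intent can be recovered from context. The value of the threshold, the superiority test, alpha, sample size and power are not in question. The point should still be fixed, because it concerns a stated decision rule for the primary endpoint.

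The conclusion rests on the SAP's own conversion formulas and the protocol's own anchor, with no assumed means. It covers only the visible wording of section 6.

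**What to change.** In Protocol 6.1 and in 6.2 items 1 and 2, replace the undirected threshold with: *is 0.20 LogMAR or better (mean ≤ 0.20)*. This matches the form already used in 6.2 item 4, and stating the inequality leaves nothing to infer.

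Then confirm that Protocol 20.2 and the decision rules of SAP 5.1, 5.2.1 and 5.2.2 use the same inequality.

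The cost is three phrases and one consistency check. Nothing changes in the tests, alpha, sample size or power.
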